Appendix 1 describes the detailed study visits, measurements, and dosing information.

5 Study Parameters

5.1 Primary Endpoint

The primary endpoint is the incidence of adverse events. The primary endpoint will be summarized based on the safety population.

5.2 Safety Measure

The safety measure is the adverse events. The safety measures will be summarized based on the safety population.

6 Sample Size Determination and Power Calculation

7 Randomization

Not applicable

8 Statistical Analysis

8.1 General Consideration

All data, including demographic and baseline characteristics and endpoint measures, will be summarized descriptively. Continuous variables will be summarized using the number of subjects (n), mean, SD, median, 25th and 75th percentiles, and minimum and maximum. Categorical variables will be summarized with frequency and percentage.

For the summaries, medical history and AEs will be coded using version 26.0 of the MedDRA dictionary.

All collected data will be presented in listings which will be sorted by subject ID and visit when it is appropriate. Summaries and data listings will be generated using SAS[®] Version 9.4 or higher.

8.2 Analysis Populations

8.2.1 Safety population

The safety population will include all enrolled subjects who received at least one Tyrvaya® administered with the nasal guide.

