#### 8.9 Monitoring and Quality Assurance

9 SAFETY DEFINITIONS, MONITORING AND REPORTING

#### 9.1 Adverse Events

An adverse event (AE) is defined as any untoward medical occurrence associated with the use of a drug or device in humans, whether the event is considered drug or device related or not. An AE can therefore be any unfavorable and unintended sign (e.g., an abnormal laboratory finding), symptom, or disease occurring after the subject started dosing with the device, without any judgment about causality. Any pre-existing medical condition that worsens after administration of the nasal guide will also be considered a new AE.

AE collection will start following the first administration of Tyrvaya® utilizing the nasal guide until the last follow up visit of the study.

Documentation regarding the AE should be made as to the nature, date of onset, end date, severity, relationship to study drug, action(s) taken, seriousness, and outcome of any sign or symptom observed by the Investigator or reported by the subject upon indirect questioning.

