# 9.2 Serious Adverse Events

An AE is considered a serious adverse event (SAE) if, in the view of either the Investigator or Sponsor, it results in any of the following outcomes:

- Death
- A life-threatening AE

Note: An AE is considered "life-threatening" if, in the view of either the Investigator or Sponsor, its occurrence places the patient or subject at immediate risk of death. It does not include an AE that, had it occurred in a more severe form, might have caused death.

• Inpatient hospitalization or prolongation of existing hospitalization

Note: The term "inpatient hospitalization" refers to any inpatient admission (even if less than 24 hours). For chronic or long-term inpatients, inpatient admission includes transfer within the hospital to an acute/intensive care inpatient unit. Inpatient hospitalization does not include emergency room visits; outpatient/same day/ambulatory procedures; observation/short stay units; rehabilitation facilities; hospice facilities; nursing homes; or clinical research/phase 1 units.

Note: The term "prolongation of existing hospitalization" refers to any extension of an inpatient hospitalization beyond the stay anticipated or required for the reason for the initial admission as determined by the Investigator or treating physician.

Note: Planned hospital admissions or surgical procedures for an illness or disease that was present before the patient received any study drug are not to be considered SAEs unless the condition deteriorated in an unexpected manner during the trial (e.g., surgery was performed earlier than planned).

• A persistent or significant incapacity or substantial disruption of the ability to conduct normal life functions.

Note: An SAE specifically related to visual threat would be interpreted as any potential impairment or damage to the subject's eyes (e.g., hemorrhage, retinal detachment, central corneal ulcer, or damage to the optic nerve).

• A congenital anomaly/birth defect in an offspring of a study subject.

Important medical events that may not result in death, are life-threatening, or require hospitalization may be considered serious when, based upon appropriate medical judgment, they may jeopardize the patient or subject and may require medical or surgical intervention to prevent one of the outcomes listed in this definition.

SAEs are collected at the time the subject signs the Informed Consent Form until the last follow up visit of the study.

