# **12 REFERENCES**

# **13. APPENDICES**

# **Appendix 1: Nasal Guide Instructions for Use**

# Nasal Guide

**Intended Purpose:** Nasal Guide is an optional accessory that helps you administer TYRVAYA® (varenicline solution) Nasal Spray by pointing the spray tip in the correct direction inside the nose and ensuring the tip doesn't go too far into the nose. For use only with TYRVAYA, as prescribed by your doctor.

Instructions for Use: Before using Nasal Guide, read these instructions and the Instructions for Use supplied with TYRVAYA. Do not discard these instructions. If you have questions, please ask your doctor or your pharmacist. Keep accessory out of the reach of children. Prepare TYRVAYA for use including priming steps per the Instructions for Use.

Attach Nasal Guide to TYRVAYA.

- Remove the blue cap from the Tyrvaya nasal applicator.
- Ensure the clip is on prior to attaching the Nasal Guide.
- Slide Nasal Guide down over the tip of the nasal applicator to sit flat against the base of the nasal applicator.
- Remove the clip.

2

Position TYRVAYA correctly.

- When ready to spray TYRVAYA into your nostril, point the arrow on Nasal Guide towards the ear on the same side as your nostril.
- Insert TYRVAYA into the nostril until Nasal Guide touches the bottom of the nose. Administer TYRVAYA per the Instructions for Use.

3

Remove and store Nasal Guide.

- Slide Nasal Guide up from the nasal applicator.
- Wipe Nasal Guide with a clean tissue.
- Store Nasal Guide in its bag until the next use.
- Wipe the TYRVAYA nasal applicator with a clean tissue. Replace the clip and the cap as per the TYRVAYA Instructions for Use.
- The Nasal Guide can be cleaned weekly by soaking for 15 minutes in a mild solution of liquid dish detergent and lukewarm water. Agitate gently. Rinse with clean water and dry with a clean tissue. DO NOT PLACE IN DISHWASHER.

Remove Nasal Guide

© 2022 Oyster Point Pharma, Inc.

Nasal Guide and TYRVAYA® are trademarks of Oyster Point Pharma, Inc. in the United States and certain jurisdictions. All rights reserved.

Manufactured for and distributed by: Oyster Point Pharma, Inc., [name]. [name].

OYSTER © 2022 Oyster Point Pharma, Inc. Oyster Point®, the Oyster Point logo, Tyrvaya®, and the Tyrvaya logo are trademarks of Oyster Point Pharma, Inc. in the United States and certain jurisdictions. All rights reserved.

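### AE collection, the safety population and the TEAE reference all start at a delivered Tyrvaya dose, so a non-serious event during guide positioning that prevents any spray is left out of the primary endpoint

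*SAP*

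**What the plan says.** The objective in both documents is the safety of the guide, and the SAP Synopsis lists the guide as the investigational product. Three definitions decide which events count towards that objective.

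- **Collection window.** Protocol 9.1: "AE collection will start following the first administration of Tyrvaya ® utilizing the nasal guide until the last follow up visit of the study".
- **Analysis population.** SAP 8.2.1: "The safety population will include all enrolled subjects who received at least one Tyrvaya® administered with the nasal guide". Protocol 10.2.1 says the same, and SAP 5.1 summarizes the primary endpoint on this population.
- **Treatment emergence.** Protocol 10.3.2 and SAP 8.10.1 judge an event as new or worsened relative to the first dose of study drug.

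Other wording in Protocol 9.1 is tied to the device. The AE definition covers any "disease occurring after the subject started dosing with the device, without any judgment about causality", and the section adds: "Any pre-existing medical condition that worsens after administration of the nasal guide will also be considered a new AE".

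Serious events follow a separate rule in Protocol 9.2: "SAEs are collected at the time the subject signs the Informed Consent Form until the last follow up visit of the study".

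In Appendix 1 of the protocol, the subject attaches the guide and aims it, and then follows this step: "Insert TYRVAYA into the nostril until Nasal Guide touches the bottom of the nose". The spray comes after that. Protocol 8.6.2 allows discontinued subjects to be replaced.

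**The concern.** Use of the test article begins before the event that opens the AE window and admits a subject to the analysis. If positioning the applicator with the guide causes pain or bleeding and the subject gives up without spraying, the event that kept the subject out of the analysis is the kind of event the study exists to count. Exclusion then depends on the outcome.

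Protocol section 3 hypothesizes that the guide adds no safety problem beyond those of Tyrvaya alone, and the results are set descriptively against historical Tyrvaya data. Leaving out a subject who had an event can only move that comparison towards the hypothesis. With 30 subjects and no inferential test, a single device-related event is a visible part of the result.

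**Working it through.** The documents contain no sample-size or power figure to reproduce (Protocol 10.3.1 says none was calculated). The check has two parts: trace one subject through the definitions, then size the effect.

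**Starting points side by side**

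| Item | Starts at | Where |
|---|---|---|
| Use of the guide | Attachment and positioning, before the spray | Protocol Appendix 1 |
| Non-serious AE collection | After the first dose given through the guide | Protocol 9.1 |
| AE definition | Start of dosing with the device | Protocol 9.1 |
| Worsening of an existing condition | Administration of the guide | Protocol 9.1 |
| SAE collection | Consent | Protocol 9.2 |
| Safety population | One dose given through the guide | Protocol 10.2.1, SAP 8.2.1 |
| TEAE reference | First dose of study drug | Protocol 10.3.2, SAP 8.10.1 |

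No section defines a window or population by attempted use of the guide.

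**Tracing one subject.** Take an enrolled subject who has a nosebleed while positioning the applicator at Visit 1 and never sprays.

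1. Non-serious event: it precedes the collection start, there is no first dose against which to call it treatment-emergent, and the subject is not in the safety population.
2. Serious event: it is collected, but the subject is still outside the population used for the summaries (SAP 5.1 and 5.2).
3. The subject may be replaced, which brings the dosed count back to 30.

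**Size without replacement.** Inputs: 30 enrolled (Protocol 5.1); one such subject (assumption); k of the other 29 have at least one AE (assumption, since the documents give no AE rate).

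- Attempted-use incidence: (k + 1)/30
- Incidence under the current definitions: k/29
- Difference: (k + 1)/30 − k/29 = [29(k + 1) − 30k]/870 = (29 − k)/870

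| k | Current | Attempted use | Difference (points) |
|---|---|---|---|
| 0 | 0/29 = 0% | 1/30 = 3.3% | 29/870 = 3.3 |
| 10 | 10/29 = 34.5% | 11/30 = 36.7% | 19/870 = 2.2 |
| 15 | 15/29 = 51.7% | 16/30 = 53.3% | 14/870 = 1.6 |
| 20 | 20/29 = 69.0% | 21/30 = 70.0% | 9/870 = 1.0 |

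The difference is never negative for k from 0 to 29, so the direction is fixed.

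**Size with replacement.** If m of the 30 dosed subjects have an AE, the difference is (m + 1)/31 − m/30 = (30 − m)/930. That is 3.2 points at m = 0 (0/30 against 1/31) and 1.6 points at m = 15.

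**How likely is at least one such subject?** The documents give no rate. For an assumed per-subject probability p, the chance among 30 is 1 − (1 − p)^30: 26% at p = 1%, 45% at 2%, 79% at 5% and 96% at 10%. If p is essentially zero, nothing is lost.

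**The case against.** The case on the other side has real force.

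- **A dosed population fits the question.** The objective concerns the guide during Tyrvaya administration, and the Protocol Synopsis describes the study treatment as the drug given with the guide. This is a reasonable convention, but it still leaves out the stage of use that comes before the dose.
- **The window is very short.** It covers only the first positioning at Visit 1, in clinic, in a subject who never sprays afterwards. Every later attachment over 7 days of twice-daily use falls inside the window. This stands and limits the severity.
- **The subject would remain visible.** SAP 8.6 calls for a by-subject listing of reasons for exclusion and summarizes discontinuation reasons among enrolled subjects, including non-fatal AE. AE queries are scheduled at Visit 1 and early termination, and SAP 8.10.1 lists all AEs with a TEAE flag. This stands too, but none of it puts the event into the primary endpoint.
- **Administration is undefined.** It could be read to include attachment and positioning, and the device-based wording in Protocol 9.1 leans that way. That is a reason to settle the wording, since the text can be read both ways.

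A reader might also infer more than the documents support:

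- *That the guide itself enters the nostril.* Appendix 1 has the applicator tip enter while the guide stops at the bottom of the nose. Before the spray, contact by the guide is external, although tip injury from poor positioning remains possible.
- *That a badly seated guide is a lost AE.* Without symptoms it is a use problem, not an untoward medical occurrence, and would not count under any window.
- *That events just before the first spray are also lost in subjects who then spray.* SAP 8.3 works by date and uses no day 0, so an event recorded on the day of the first dose is naturally Dosing Day 1. The point does not rest on these subjects.
- *That each affected subject always costs about 3 percentage points.* That holds only when almost nobody else has an AE.

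**Conclusion.** The point holds as a narrow definitional gap of minor severity. Followed as written, the plan omits from the primary endpoint a subject whose non-serious AE during positioning prevents any spray, and it treats a serious event in such a subject as collected but not summarized. Any resulting bias runs one way, towards finding the guide harmless.

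One such subject among 30 lowers any-AE incidence by at most 3.3 percentage points, and by 1.6 points if 15 other subjects have AEs. These figures assume exactly one such subject and a chosen background count, neither of which the documents supply; the true number may be 0. The documents do not support a claim that the result will be materially wrong or that such a case would be hidden from the reader.

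**What to change.** 1. **Protocol 9.1:** reconcile the drug-based and device-based wording, and start AE collection at the first attempted use of the guide (attachment or positioning) at Visit 1.
2. **Protocol 10.2.1 and SAP 8.2.1:** define the safety population as all enrolled subjects who attempted at least one administration with the guide, whether or not a spray was delivered.
3. **Protocol 10.3.2 and SAP 8.10.1:** reference treatment emergence to that first attempt.

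The cost is a few sentences across the two documents. No new visit, procedure or subject is needed, because an AE query already takes place at Visit 1. The one drawback is that the denominator may differ slightly from that of the historical Integrated Summary of Safety, which cannot be checked from these documents. Reporting the dosed-subject count alongside the attempted-use count deals with that.

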8.3 Definition of Study Day or Dosing Day

Study and dosing days are defined as follows:

Study Day =	[Event date – Informed consent date + 1] if after informed consent date. [Event date – Informed date] if before informed consent date.
Dosing Day=	[Event date – First dosing date + 1] if after first dosing date. [Event date – First dosing date] if before first dosing date.

Note that with the definition above, days of "0" will not be used.

For subjects whose reference date is missing, the study day will also be categorized as missing.

Adverse event onset

If onset date is completely missing, date is set to date of first dose.

If year is present and month and day are missing or year and day are present and month is missing:

- If year = year of first dose, then set month and day to month and day of first dose.
- \circ If year < year of first dose, then set month and day to December 31.
- \circ If year > year of first dose, then set month and day to January 1.

If month and year are present and day is missing:

- \circ If year = year of first dose and
 - month = month of first dose, then set day to day of first dose date.
 - month < month of first dose, then set day to last day of month.
 - month > month of first dose, then set day to first day of month.
- \circ If year < year of first dose, then set day to last day of month.
- \circ If year > year of first dose, then set day to first day of month.

For all other cases, set date to date of first dose.

Adverse event end date

If year is present and month and day are missing or year and day are present and month is missing, set end month and day to December 31.

If month and year are present and day is missing, set the day to last day of the month. If fatal event, date is set to minimum of imputed end date and death date. For all other cases, set date to missing.

For summaries that present distribution of time expressed in weeks and months, weeks will be defined as days divided by 7 and months as days divided by 30.4375.

8.5 **Protocol Deviation**

8.6 Subject Disposition

The number and percentage of subjects enrolled and included in sa

will be summarized. Reasons for excluding subjects from the analysis populations will be presented in a by-subject listing.

The number of enrolled subjects who completed the study, discontinued early from study, completed the treatment, discontinued early from the treatment, and reasons for discontinuation will be summarized.

The Case Report Form (CRF) lists the following reasons why subjects may discontinue treatment or discontinue study:

- Non-Fatal Adverse Event
- Protocol Violation
- Lost to Follow Up
- Pregnancy
- Disease Progression
- Physician Decision
- Subject Non-Compliance
- Death
- Study Terminated by Sponsor
- Withdrawal by Subject
- Other

8.7 Demographics and Baseline Characteristics

The following demographic will be summarized based on safety population:

- Age
- Gender
- Ethnicity
- Race

8.8 Medical History, Medical Procedure and Ocular History

Medical history terms, medical procedure terms and ocular history terms will be coded using the Medical Dictionaryfor Regulatory Activities (MedDRA) version 26.0 and the number and percent of subjects with medical history will be summarized by (SOC) and Preferred Term (PT) based on the safety population.

8.9 Treatment Exposure

Duration of exposure to study treatment, in days, will be summarized for all safety subjects.

8.10 Safety Analysis

8.10.1 Adverse Event

The investigator will promptly review each Adverse Event (AE) for accuracy and

completeness, and classify each AE according to its intensity, its re

administration procedure, and its seriousness. AEs will be coded using version 26.0 of the MedDRA dictionary. AEs will be monitored throughout the study and documented on the appropriate AE form. AEs will be categorized as ocular and non-ocular events as well as by system organ class (SOC) and preferred term (PT), seriousness, severity, and relation to study medications.

All treatment-emergent adverse events (TEAEs) will be summarized. A TEAE is defined as an AE that is new or worsened in severity compared to the first dose of study drug.

TEAEs will be summarized by subject. In addition, the number of TEAE episodes that occurred during the study will be provided in the overall summary of AE table. All AEs will be presented in data listing with a flag indicating the event is a TEAE.

The following presentations of TEAEs will be generated:

- Overall adverse events summary (including any TEAEs, ocular TEAEs, resolved ocular TEAEs, non-ocular TEAEs, SAEs, treatment emergent SAEs, treatment-related treatment emergent SAEs, TEAEs by maximum severity, TEAEs by relationship to study drug, AEs leading to treatment/study discontinuation)
- All TEAEs by SOC and PT
- All ocular TEAEs by SOC and PT
- All non-ocular TEAEs by SOC and PT
- Resolved ocular TEAEs by SOC and PT
- Serious adverse events (SAE) by SOC and PT
- Serious treatment-emergent adverse events (TESAE) by SOC and PT
- Related treatment-emergent serious adverse events (TESAE) by SOC and PT
- TEAEs by SOC and PT and by severity
- TEAEs by SOC and PT and by relationship
- TEAEs by SOC and PT leading to treatment discontinuation
- TEAEs by SOC and PT leading to study discontinuation

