# **10.3** Statistical Analysis

This section briefly outlines the planned analyses. The statistical analysis plan (SAP) describes the methods to be used in detail. If the SAP and the protocol disagree, the details and methods of the SAP will prevail.

The AE data collected from this study will be compared with the historical AE data collected for Tyrvaya® alone from OC-01 (varenicline solution) nasal spray Integrated Summary of Safety (ISS). The data comparison will be presented descriptively without inferential statistics comparison.

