8.10 Safety Analysis	
Appendix 1 Schedule of Visits and Measurements	

1 Synopsis

Protocol Title:	A Phase 4, Single-Center, Open-Label Study Evaluating the Safety of the Nasal Guide Utilized During Administration with Tyrvaya®
Protocol Number:	OPP-009
Investigational Product:	Nasal guide
Study Objective:	To determine the safety of the nasal guide when utilized to aid in the administration of Tyrvaya® (varenicline solution 0.03 mg) Nasal Spray
Treatment Assignment	30 subjects will be provided the nasal guide to utilize with Tyrvaya® administration.
Sample Size and Power	
Randomization and Stratification	Not applicable
Study Endpoints	Primary endpoints Incidence of adverse events
Statistical Analysis for Primary Endpoint	The AE data collected from this study will be summarized with frequency and percentage. The profile of the adverse events will be made by comparing the results from this study with the external historical AE data collected for Tyrvaya® alone from OC-01 (varenicline solution) nasal spray Integrated Summary of Safety (ISS). The data comparison will be made without inferential statistics.
Analysis Population	

Abbreviations

AE	adverse event
BID	two times a day
FDA	Food and Drug Administration
HIPAA	Health Information Portability and Accountability Act
ICH	International Conference on Harmonization
MedDRA	medical dictionary for regulatory activities
mg	Milligram
SAE	serious adverse event
SAE SAP	serious adverse event Statistical Analysis Plan
2112	
SAP	Statistical Analysis Plan
SAP SD	Statistical Analysis Plan Standard deviation

2 Introduction

This statistical analysis plan (SAP), which is based on the original protocol of the study protocol dated May 02, 2023, defines the methods, and analyses that Oyster Point Pharma, Inc. (henceforth, Oyster Point) plans to use to analyze and summize the data from Protocol OPP-009. This SAP complies with guidance promulgated by the International Conference on Harmonization (ICH) and the US Food and Drug Administration (FDA). If the protocol is subsequently amended, this SAP may be amended as well. Should the SAP and the protocol be inconsistent with respect to the planned analyses, the language of the SAP prevails.

3 Study objective

The objective of this study is to determine the safety of the nasal guide during administration of Tyrvaya® (varenicline solution 0.03 mg) Nasal Spray.

4 Study Design

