8.10.2 Concomitant Medications

Concomitant medications will be coded using the World Health Organization Drug Dictionary (March 2023 version) and summarized in the safety population. Any medication taken from the day of first dose of the study treatment up to the day of last date of the study will be considered as a concomitant medication for analysis.

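### Does pooling earlier Tyrvaya users with new starters, with no table showing the mix, undermine the comparison with the ISS data?

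*SAP*

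**What the plan says.** The primary endpoint is the incidence of adverse events, and "The primary endpoint will be summarized based on the safety population" (SAP 5.1). Treatment emergence is judged against the start of study dosing: "A TEAE is defined as an AE that is new or worsened in severity compared to the first dose of study drug" (SAP 8.10.1). The tables, such as "All TEAEs by SOC and PT", are for one pooled group.

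The SAP synopsis plans to profile the events by "comparing the results from this study with the external historical AE data collected for Tyrvaya® alone", taken from the Integrated Summary of Safety (ISS). Protocol 10.3 limits how far this goes: "The data comparison will be presented descriptively without inferential statistics comparison".

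Three other outputs bear on the point:
- SAP 8.7 introduces its baseline list with "The following demographic will be summarized based on safety population" and names age, gender, ethnicity and race.
- SAP 8.9 states: "Duration of exposure to study treatment, in days, will be summarized for all safety subjects".
- SAP 8.10.2 defines a concomitant medication as "Any medication taken from the day of first dose of the study treatment up to the day of last date of the study".

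Prior medication is recorded at Visit 1 (Protocol 8.3.1). SAP 8.1 commits to summarising all data descriptively and to listing all collected data by subject.

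**The concern.** Nothing in the visible text keeps out people who already use Tyrvaya. Protocol 5.4 has no exclusion criteria, 8.1.3 no washout and 8.2.1 no prohibited medications. The clinical hypothesis in Protocol 3 is that the guide adds no safety concern to those of Tyrvaya alone. There is no concurrent control, so the historical comparison carries much of the weight.

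Suppose established users and new starters were both enrolled. An established user with a steady drug effect at Visit 1 has nothing new or worse to report, whereas a new starter who develops that effect adds to the count. Pooling could then lower the observed incidence and make the guide look more reassuring than it is. The baseline table does not list earlier use, the exposure table covers study treatment only, and the medication table starts at the first study dose, after which every subject is on Tyrvaya. A reader of the named tables could not see the mix.

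**Working it through.** The plan gives no figure to reproduce. The sample size of 30 has no formal basis (Protocol 10.3.1), and the documents give no event rates, no share of earlier users and no description of the ISS population. The check therefore takes each condition the concern needs in turn.

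**1. Are both user types admitted?** The inclusion criteria are numbered 1, 3 and 5 in both the Protocol synopsis and section 5.3, so items 2 and 4 are not visible. The visible items cannot be the whole rule: the synopsis gives dry eye disease as the condition, yet no visible item requires it. Text that is not visible cannot be counted as missing from the plan, and either item could settle earlier Tyrvaya use.

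The remaining hints are these:
- the synopsis calls this a sub-study;
- Tyrvaya is the commercial product (Protocol 11.5.1);
- Visit 1 dispenses the guide but lists no dispensing of Tyrvaya (8.3.1);
- the inventory described is for the guide (11.5.3).

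None is proof. To the extent that they show anything, they suggest subjects who already have Tyrvaya, which is one user type and not a mixture.

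**2. Would events in earlier users go uncounted?** Only in part. Protocol 9.1 counts any unfavourable sign or symptom that occurs after dosing with the device begins, whatever its cause, and also the worsening of an existing condition. A steady, continuous effect would not count. A symptom that returns after each guide-assisted spray may count. The documents do not show which pattern applies.

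**3. Would the ISS comparison be distorted?** Only if ISS subjects were mainly new starters. The documents do not say.

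**4. Size under assumed inputs.** Let *p* be the incidence in new starters, *f* the share of earlier users and *r* the ratio of their incidence to *p*. Then

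pooled incidence = (1 − f)·p + f·r·p = p·[1 − f(1 − r)].

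The factor multiplying *p* is:

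| f | r = 0.5 | r = 0.75 | r = 1 |
|---|---|---|---|
| 0.25 | 0.875 | 0.9375 | 1 |
| 0.50 | 0.75 | 0.875 | 1 |
| 0.75 | 0.625 | 0.8125 | 1 |

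Expected subjects with an event, 30·p·[1 − f(1 − r)], at f = 0.5:

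| p | r = 1 | r = 0.75 | r = 0.5 |
|---|---|---|---|
| 20% | 6 | 5.25 | 4.5 |
| 50% | 15 | 13.1 | 11.25 |
| 80% | 24 | 21 | 18 |

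The arithmetic is sound, but *p*, *f* and *r* are all assumed. Capping *r* at 1 is also an assumption, and it lets the shift run in one direction only. The shift is zero if r = 1 or if no earlier users enrol.

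**5. What would a split show?** Exact (Clopper-Pearson) 95% intervals are 31.3% to 68.7% for 15/30, 26.6% to 78.7% for 8/15 and 18.7% to 81.3% for 5/10. The factor of 0.75 from step 4 (f = 0.5, r = 0.5) takes 50% to 37.5%, well inside the interval for 8/15. A split could display the mix but could not measure a bias of this size.

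**The case for a change.** The strongest reply is that the concern is conditional and its checkable part is true: no named table counts earlier users or splits events by earlier use. The study has no control group and no test, so its conclusion depends on readers judging comparability, and any error would be in the reassuring direction. One baseline row and one descriptive split would cost little.

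The factual part stands: the named tables do not show the mix. The rest is weaker.
- The general commitment in SAP 8.1 to summarise all data covers prior medication, although no specific table is named. With by-subject listings for 30 subjects, a hand count is feasible if earlier Tyrvaya use is recorded as prior medication. The documents do not say that it is, nor do they show a look-back window, so a split could not be assumed to come free from existing data.
- The ISS comparison is not the only evidence on the hypothesis. Protocol 10.3.2 has the investigator classify each event by its relation to the drug or the administration procedure, and SAP 8.10.1 tabulates events by relationship. Earlier users remain informative about harm caused by the guide itself.
- If entry is limited to one user type, the split is empty. If that type is current users, this would be a point for interpreting the ISS comparison, not a fault in the planned tables.

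**Conclusion.** The concern does not hold. Following the plan as written is not shown to give a wrong or worse result. Harm needs three things together: a mixed population, drug effects in earlier users that persist rather than recur, and an ISS population made up mainly of new starters. The first turns on inclusion items that are not visible, and the visible hints lean away from it. The documents settle neither of the others.

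The possible size is a pooled incidence of 0.625 to 1.0 times the starter incidence, for an assumed 25% to 75% of earlier users with an event rate 0.5 to 1 times that of starters. That range includes no effect. The comparison is descriptive, in a pilot with no test and no visible decision threshold, and a split of 30 subjects could not measure the bias. A count of earlier users would be a reasonable courtesy to readers if both types do enrol, but it would not change what the trial does or can conclude.

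This rests on treating items 2 and 4 as part of the plan although they cannot be read here. If they do admit both user types, the first condition is met and the other two remain open.
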